6 RADIATION THERAPY GUIDELINES

6.1 Dose, Fractionation and Constraints

When feasible it is strongly recommended that radiotherapy begin on a Monday. It is accepted that occasional logistical delays may occur during radiotherapy treatment due to

machine downtime or other issues. Radiotherapy as administered during this study may take up to 10 business days without being considered a protocol deviation.

Radiotherapy will consist of five fractions, delivered once daily, to a total dose of 25 Gy at 5 Gy per fraction (PTV2500). Daily imaging to verify accurate setup is mandatory. It is required that at least 95% of the PTVs receive at least 95% of the prescription dose and that the maximum dose be $\leq 115\%$ of the prescription dose. Every effort should be made for 100% of the PTV to be covered by 95% of the prescription dose. The maximum allowed dose to small bowel is 25 Gy.

An optional concomitant boost may be delivered to the primary tumor of 1-2 Gy per day (30-35 Gy to tumor total). If a boost is given then the maximum allowed dose to small bowel is 25 Gy. Lymph nodes that are outside of the mesorectum may be boosted up to 35 Gy in 5 fractions also, as long as this small bowel constraint is met.

The following constraints are recommended when boosting lymph node or primary:

Bladder V20Gy < 15 cc. Dmax < 38 Gy.

Penile bulb V30Gy < 3 cc.

Femoral heads V30Gy < 10 cc.

Skin V36.5Gy < 10 cc. Dmax < 38.5 Gy.

6.2 Treatment Planning Procedures

Image-based treatment planning and intensity modulated radiotherapy (IMRT) is permitted. Proton therapy is not permitted. Dose volume histogram (DVH) information for the target volumes, small bowel, and uninvolved colon (defined to be large bowel outside the clinical target volumes) is mandatory. This is to assist in interpreting outcome, including morbidity.

6.3 Simulation Procedures/Patient Positioning

The prone position with a bowel displacement device incorporated into the immobilization cast is generally recommended as the best way to exclude small bowel from the pelvis. The exceptions would be patients unable to lay prone or morbidly obese patients whose diagnostic supine CT scans demonstrate little or no small bowel in the pelvis. Those patients with good bladder control should be treated with a full bladder to further exclude small bowel. All patients should be simulated with oral small bowel contrast.

6.4 Clinical Target Volume (CTV) and Planning Target Volume (PTV) Definitions

CTV2500 should include rectum and associated mesentery extending caudad at least to two cm below the distal edge of palpable disease. Superiorly it should include the rectum and its mesentery to the level of the rectosigmoid or two cm proximal to macroscopic disease, whichever is more cephalad. In addition, the internal iliac, internal obturator, and pre-sacral lymph node regions should be included. Contouring should be as per the RTOG

anorectal contouring atlas (www.rtog.org).

If the concomitant boost is prescribed then the GTV3500 is defined by radiographic findings and clinical exam, as per treating physician judgment. Pelvic MRI is required for patients to receive boost.

PTV2500 is generated by a uniform 0.7 cm expansion about CTV2500. PTV expansion for boost is 1-1.5 cm expansion off of the GTV (including mesorectum at the axial level of the GTV is at physician's discretion). In order for this tight PTV margin to be used, it is required that a physician review daily setup images for each of the five fractions.

6.5 Normal Tissue Contours

Small bowel and uninvolved colon should be contoured tightly. Uninvolved colon is defined to be large bowel that lies outside the CTV. Colon that lies within the CTV (rectum and parts of the sigmoid) is a target structure, not an avoidance structure, hence its exclusion from "uninvolved colon." The CTV is NOT to be extracted from small bowel. If small bowel lies within a CTV, that WILL contribute to the small bowel dose. Since absolute rather than relative bowel volumes are to be tracked, it is not necessary to contour the entire large and small bowel, only those loops caudal to 1 cm above the most cephalad extent of CTV2500.

7 CHEMOTHERAPY GUIDELINES

7.1 Chemotherapy Schedule and Doses

Chemotherapy should begin 2 to 4 weeks after completion of radiotherapy and will consist of 5FU/leucovorin/oxaliplatin every other week for 8 courses (16 weeks). Alternatively, capecitabine/oxaliplatin (CAPE PO 1000 mg/m² BID days 1-14 Q21 days, oxaliplatin IV 130 mg/m² IV Q21 days on day 1) x 5 cycles over 15 weeks may be administered instead of FOLFOX. A maximum (total) delay of treatment of 4 weeks is allowed per protocol due to factors/AEs listed in this section. Cumulative delays in excess of 4 weeks will need to be discussed with the Principal Investigator. Such cases will need to be individualized depending on the clinical scenario.

7.2 Agent Administration

Folfox	Dose	Route	Schedule
Oxaliplatin*	85 mg/m ²	IV over 2 hours	On Day 1, Q 14 days
Leucovorin*	400 mg/m ²	IV over 2 hours	On Day 1, Q 14 days
5-FU Bolus*	400 mg/m ²	IV push	On Day 1, Q 14 days
5-FU Infusion*	2400 mg/m ²	IV CIIV	On Day 1, Q 14 days over 46 hours

*Administer sequentially as written, except oxaliplatin and leucovorin may be administered concurrently

CapeOx	Dose	Route	Schedule
Oxaliplatin	130 mg/m ²	IV	On Day 1, Q 21 days
Capecitabine	1000mg/m ²	PO BID	On Days 1-14, Q 21 days

Dose calculations should be based on actual weight and not corrected for obesity.

7.3 Supportive Care Recommendations

Veno-occlusive disease is a very rare AE associated with the administration of the combination of 5-FU and oxaliplatin. VOD disease is characterized by hepatomegaly, ascites, and jaundice. These signs and symptoms should prompt consideration of VOD. A Doppler ultrasound showing reversal of portal blood flow or other evidence of portal hypertension is suggestive of this diagnosis. In addition, standard clinical practice for evaluation of VOD should include observation of liver and spleen size, history of or gastrointestinal bleeding, development of esophageal varices, ascites, bleeding, or jaundice. All patients on and off therapy who develop signs and symptoms suggestive of VOD should be thoroughly evaluated and closely monitored and supported as clinically dictated.

Grade 3/4 hypersensitivity, including anaphylactic/anaphylactoid reactions, has been observed with oxaliplatin. These allergic reactions, which can be fatal, can occur within minutes of administration, and can occur during any cycle. There were similar in nature and severity to those reported with other platinum-containing compounds, such as rash, urticaria, erythema, pruritus, and rarely bronchospasm and hypotension. These reactions are usually managed with standard epinephrine, corticosteroid, and antihistamine therapy, and require discontinuation of therapy.

Ice should be avoided during the infusion of oxaliplatin because cold temperatures can exacerbate acute neurological symptoms.

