8 DOSE DELAYS/DOSE MODIFICATIONS

Radiotherapy for this trial may take place over a maximum of 10 business days before it is considered a protocol deviation. There are no dose adjustments (reductions, omissions) associated with radiotherapy.

All toxicities should be graded according to the Common Terminology Criteria for Adverse Events (CTCAE), version 4.0. Dose modifications are based upon dose level administered at last treatment day. If the dose level has been reduced due to toxicity, re-escalation is not permitted. If dose reduction is required after dose level -3, patient will discontinue protocol therapy.

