8.2 Dose Modifications for Toxicity Related to FOLFOX and CapeOx

The provided dose modifications are strongly recommended. However, out of consideration of unforeseen clinical scenarios, dose modifications during FOLFOX chemotherapy are ultimately at the discretion of the primary treating provider. The use of 5-FU bolus is at the discretion of the treating physician. Modifications should be reported to the research coordinator. Refer to table 8.2 and 8.3 for guidance regarding suggested dose reductions and treatment delays, consistent with best oncologic practices.

Toxicity NCI Grade (Value)	Worst interval toxicity	Day of treatment
Neutropenia (ANC)		
Grade 1 (ANC < LLN – 1500/mm ³)	Maintain dose level	If ANC < 1000 on day of treatment, hold and check weekly until ≥ 1000 mm ³ . Then treat based on interval toxicity. If ANC < 1000 after 4 weeks, discontinue therapy.
Grade 2 (ANC < 1499 – 1000/mm ³)		
Grade 3 (ANC < 999 – 500/mm ³)	Reduce 1 dose level	
Grade 4 (ANC < 500/mm ³)		
Thrombocytopenia		
Grade 1 (PLT < LLN – 75,000/mm ³)	Maintain dose level	If PLT < 75,000 on day of treatment, hold and check weekly until ≥ 75,000 mm ³ . Then treat based on interval toxicity. If PLT < 75,000 after 4 weeks, discontinue therapy.
Grade 2 (PLT 74,999 – 50,000/mm ³)		
Grade 3 (PLT 49,999 – 25,000/mm ³)	Reduce 1 dose level	
Grade 4 (PLT < 25,000/mm ³)		
Diarrhea		
Grade 1	Maintain dose level	Hold chemotherapy if any grade of diarrhea above grade 1 is present with the patient not taking antidiarrheal agents within 24 hours of treatment. Reduce 5-FU and oxaliplatin 1 dose level upon resolution of diarrhea. If diarrhea has not resolved within 4 weeks of scheduled treatment day, discontinue therapy.
Grade 2		
Grade 3		
Grade 4		
Other nonhematologic toxicities (except neurologic, alopecia, anorexia, nausea/vomiting if can be controlled by antiemetics)		
Grade 1	Maintain dose level	Maintain dose level
Grade 2		
Grade 3	Reduce 1 dose level	Hold until resolved to grade ≤1. Reduce 5-FU and oxaliplatin 1 dose level
Grade 4		

8.3 Dose Modifications for Neurologic Toxicity (Paresthesia or Dysesthesia) Related to Oxaliplatin

Grade	Duration of Toxicity		
	1 – 7 Days	> 7 Days	Persistent Between Doses
Grade 1 Short duration that resolves and does not interfere with function	No change	No change	No change
Grade 2 Interfering with function, but not activities of daily living (ADL)	No change	No change	Reduce oxaliplatin 1 dose level

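### The Section 8.2 catch-all row, read literally, re-doses oxaliplatin one level lower after grade 3 hypersensitivity, where Section 7.3 requires a stop

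*Combined protocol and SAP*

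**What the plan says.** Section 7.3 (Supportive Care Recommendations) covers grade 3/4 hypersensitivity to oxaliplatin, anaphylaxis included. It describes the danger as follows: "These allergic reactions, which can be fatal, can occur within minutes of administration, and can occur during any cycle". It then gives the management: "These reactions are usually managed with standard epinephrine, corticosteroid, and antihistamine therapy, and require discontinuation of therapy". It does not say whether therapy means oxaliplatin alone or the whole regimen.

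Section 8.2 covers toxicity from FOLFOX and CapeOx. It introduces its tables with "Refer to table 8.2 and 8.3 for guidance regarding suggested dose reductions and treatment delays". One row is a catch-all: "Other nonhematologic toxicities (except neurologic, alopecia, anorexia, nausea/vomiting if can be controlled by antiemetics". For grade 3, the worst-interval-toxicity column of that row reads "Reduce 1 dose level", and the day-of-treatment column reads "Hold until resolved to grade ≤1. Reduce 5-FU and oxaliplatin 1 dose level".

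Section 8 supplies two general rules. The first sets the reference dose: "Dose modifications are based upon dose level administered at last treatment day". The second sets the floor: "If dose reduction is required after dose level -3, patient will discontinue protocol therapy". Section 8.1 gives the dose ladder for each regimen. Section 8.3 deals only with paresthesia and dysesthesia.

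**The concern.** Two parts of the plan address the same event and give different actions. Section 7.3 stops treatment. The Section 8.2 row, followed as printed, continues oxaliplatin at a lower dose once the reaction has settled. Nothing in Sections 8 to 8.3 refers back to 7.3, and no text says which section prevails.

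What is at stake is the safety of individual patients. A dose-modification table is the natural place to look when choosing the next dose, and the plan provides for secondary sites, so the table should be safe to use without knowledge of a paragraph in another section. The protocol itself calls these reactions potentially fatal.

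**Working it through.** There is no statistical figure to reproduce. The check is a comparison of texts, plus one step down the dose ladder.

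**1. Does hypersensitivity fall in the catch-all row?** The event is nonhematologic. The row's exceptions are neurologic toxicity, alopecia, anorexia, and nausea or vomiting controllable by antiemetics. Hypersensitivity is not among them. It has no row of its own in 8.2 and lies outside the scope of 8.3. The allergy criterion in Section 3.2 concerns history at entry and gives no on-treatment rule. On the words of the table, the event falls in this row.

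**2. Which column applies?** A reaction at infusion that resolves before the next cycle would most naturally be scored as worst interval toxicity, although 8.2 does not define that column. The choice does not matter here. One column reduces a level; the other holds until grade ≤1 and then reduces 5-FU and oxaliplatin a level. Both end in another oxaliplatin dose.

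**3. Is a stop implied elsewhere in Section 8?** Section 8 states stops where it intends them. The neutropenia, thrombocytopenia and diarrhea rows each end therapy if the problem is unresolved after 4 weeks. Section 8.3 stops oxaliplatin for grade 4 neurotoxicity and for grade 3 that persists between doses. The catch-all row shows no stop, so a reader of the tables would not infer one.

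**4. What dose results?** Inputs are the oxaliplatin lines of Section 8.1 and the Section 8 rule that modifications start from the last administered level. The share retained is the next dose divided by the last dose.

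| Last level given | FOLFOX oxaliplatin, mg/m² | Share retained | CapeOx oxaliplatin, mg/m² | Share retained |
|---|---|---|---|---|
| Starting dose | 85→65 | 65/85 = 76% | 130→104 | 104/130 = 80% |
| -1 | 65→50 | 50/65 = 77% | 104→78 | 78/104 = 75% |
| -2 | 50→40 | 40/50 = 80% | 78→70 | 70/78 = 90% |
| -3 | stop | none | stop | none |

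At 3 of the 4 levels in each regimen the row gives a further oxaliplatin dose, at 75% to 90% of the last one. At level -3 Section 8 ends protocol therapy, so oxaliplatin stops, as under 7.3. Agreement at that level is certain only for oxaliplatin. If 7.3 means oxaliplatin alone, the two texts still differ on the fluoropyrimidine.

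**5. How far does this extend to grade 4?** The readable table shows no separate grade 4 entry in this row. A cell merged with grade 3 is the likely layout, but blank cells are not firm evidence of merging. In the diarrhea row only grade 1 has a worst-interval entry (no dose change). Carrying that entry down to grade 4 would sit oddly beside a day-of-treatment entry that reduces the dose. The mismatch is therefore shown for grade 3 and is only probable for grade 4.

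**The case against.** The strongest reply is that the plan already handles the event. Section 7.3 names this exact reaction and says what to do. A row for other toxicities can be read as covering whatever is not dealt with elsewhere, and Section 5.2 sends sites to Section 7 for chemotherapy guidance. Section 8.2 describes its modifications as strongly recommended and its tables as suggestions in line with good oncologic practice, and it leaves FOLFOX modifications to the treating provider. Section 10 adds that FOLFOX is given to standard of care and points to the package inserts.

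Much of this stands. A reader might infer that the protocol mandates rechallenge after a severe allergic reaction. The documents do not support that: the stop is stated in 7.3, which is the more specific text, and 8.2 is advisory. A reader might also infer that the re-dosing instruction is established for grade 4, and the readable table does not establish it.

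The conflict itself remains. No text ranks 7.3 above 8.2, and 7.3 is itself headed as recommendations. The discretion sentence in 8.2 names only FOLFOX, although the section heading also covers CapeOx. Advisory status lowers the practical risk, but it does not make the printed action right for an event the protocol calls potentially fatal.

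It is also fair to say that the dose steps measure the literal reading and not its clinical impact. The documents give no incidence of hypersensitivity, so no frequency can be attached.

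**Conclusion.** The inconsistency is real and minor. For grade 3 oxaliplatin hypersensitivity, Section 7.3 calls for discontinuation, while the 8.2 catch-all row leads to oxaliplatin one level lower at the starting dose, level -1 and level -2 of both regimens. Grade 4 probably follows the same entry, subject to the typeset table.

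This rests on three things: the row's exceptions are read as a closed list; hypersensitivity is counted as a nonhematologic toxicity; and no other text in the protocol overrides the row. That most clinicians would follow 7.3 is a judgement, and it is the main reason for the low rating.

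A reader might take the point as bearing on the trial's conclusions. It does not change the sample size, the 6/20 decision rule or the analysis. A patient who stops chemotherapy for this reason may be inevaluable and replaced under Section 16.4, but that already follows from 7.3.

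**What to change.** In the 8.2 row for other nonhematologic toxicities, add grade 3/4 hypersensitivity to the exceptions. Attach a footnote that applies to FOLFOX and CapeOx:

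*Grade 3/4 hypersensitivity to oxaliplatin: permanently discontinue oxaliplatin; do not dose-reduce and re-treat (Section 7.3).*

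The footnote should name the drug, because a bare reference to discontinuing under 7.3 would carry over that section's ambiguity. It should also state whether 5-FU/leucovorin or capecitabine may continue. Section 16.4 counts as evaluable only patients who complete all radiotherapy and chemotherapy, so the sponsor should say how a patient who finishes on the fluoropyrimidine without oxaliplatin is classified.

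The wording covers both grades, so it works however the grade 4 cell is laid out. The cost is one exception and one footnote in the next amendment, with no added visits or procedures.

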8 DOSE DELAYS/DOSE MODIFICATIONS

Radiotherapy for this trial may take place over a maximum of 10 business days before it is considered a protocol deviation. There are no dose adjustments (reductions, omissions) associated with radiotherapy.

All toxicities should be graded according to the Common Terminology Criteria for Adverse Events (CTCAE), version 4.0. Dose modifications are based upon dose level administered at last treatment day. If the dose level has been reduced due to toxicity, re-escalation is not permitted. If dose reduction is required after dose level -3, patient will discontinue protocol therapy.

8.1 Dose Levels

Folfox	Starting Dose	Dose Level -1	Dose Level -2	Dose Level -3
Oxaliplatin	85 mg/m ²	65 mg/m ²	50 mg/m ²	40 mg/m ²
Bolus 5-FU	400 mg/m ²	300 mg/m ²	200 mg/m ²	100 mg/m ²
Infusion 5-FU	2400 mg/m ²	1920 mg/m ²	1600 mg/m ²	1360 mg/m ²
Leucovorin	400 mg/m ²	400 mg/m ²	400 mg/m ²	400 mg/m ²

CapeOx	Starting Dose	Dose Level -1	Dose Level -2	Dose Level -3
Capecitabine	1000 mg/m ²	800 mg/m ²	600 mg/m ²	540 mg/m ²
Oxaliplatin	130 mg/m ²	104 mg/m ²	78 mg/m ²	70 mg/m ²

*Rounding capecitabine to nearest full tablet dose is acceptable (i.e. Dose 1900 mg rounded to 2000 mg (4x 500 mg tablets) daily).

8.2 Dose Modifications for Toxicity Related to FOLFOX and CapeOx

The provided dose modifications are strongly recommended. However, out of consideration of unforeseen clinical scenarios, dose modifications during FOLFOX chemotherapy are ultimately at the discretion of the primary treating provider. The use of 5-FU bolus is at the discretion of the treating physician. Modifications should be reported to the research coordinator. Refer to table 8.2 and 8.3 for guidance regarding suggested dose reductions and treatment delays, consistent with best oncologic practices.

Toxicity NCI Grade (Value)	Worst interval toxicity	Day of treatment
Neutropenia (ANC)		
Grade 1 (ANC < LLN – 1500/mm ³)	Maintain dose level	If ANC < 1000 on day of treatment, hold and check weekly until ≥ 1000 mm ³ . Then treat based on interval toxicity. If ANC < 1000 after 4 weeks, discontinue therapy.
Grade 2 (ANC < 1499 – 1000/mm ³)		
Grade 3 (ANC < 999 – 500/mm ³)	Reduce 1 dose level	
Grade 4 (ANC < 500/mm ³)		
Thrombocytopenia		
Grade 1 (PLT < LLN – 75,000/mm ³)	Maintain dose level	If PLT < 75,000 on day of treatment, hold and check weekly until ≥ 75,000 mm ³ . Then treat based on interval toxicity. If PLT < 75,000 after 4 weeks, discontinue therapy.
Grade 2 (PLT 74,999 – 50,000/mm ³)		
Grade 3 (PLT 49,999 – 25,000/mm ³)	Reduce 1 dose level	
Grade 4 (PLT < 25,000/mm ³)		
Diarrhea		
Grade 1	Maintain dose level	Hold chemotherapy if any grade of diarrhea above grade 1 is present with the patient not taking antidiarrheal agents within 24 hours of treatment. Reduce 5-FU and oxaliplatin 1 dose level upon resolution of diarrhea. If diarrhea has not resolved within 4 weeks of scheduled treatment day, discontinue therapy.
Grade 2		
Grade 3		
Grade 4		
Other nonhematologic toxicities (except neurologic, alopecia, anorexia, nausea/vomiting if can be controlled by antiemetics)		
Grade 1	Maintain dose level	Maintain dose level
Grade 2		
Grade 3	Reduce 1 dose level	Hold until resolved to grade ≤1. Reduce 5-FU and oxaliplatin 1 dose level
Grade 4		

8.3 Dose Modifications for Neurologic Toxicity (Paresthesia or Dysesthesia) Related to Oxaliplatin

Grade	Duration of Toxicity		
	1 – 7 Days	> 7 Days	Persistent Between Doses
Grade 1 Short duration that resolves and does not interfere with function	No change	No change	No change
Grade 2 Interfering with function, but not activities of daily living (ADL)	No change	No change	Reduce oxaliplatin 1 dose level
Grade 3 With pain or with functional impairment that also interferes with ADL	1 st time: reduce oxaliplatin 1 dose level	1 st time: reduce oxaliplatin 1 dose level	Discontinue oxaliplatin
	2 nd time: reduce oxaliplatin another dose level	2 nd time: reduce oxaliplatin another dose level	
Grade 4 Persistent symptoms that are disabling or life-threatening	Discontinue oxaliplatin	Discontinue oxaliplatin	Discontinue oxaliplatin

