5.2 During Radiotherapy and Chemotherapy

Routine standard of care examinations and blood work will be done. This consists of a CMP and a CBC with differential prior to each cycle of chemotherapy and examination by the radiation oncologist during the week of radiation therapy and by a medical oncology physician or nurse with each cycle of chemotherapy. Please see Section 6 for radiation therapy guidelines and Section 7 for chemotherapy guidelines.

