10 PHARMACEUTICAL INFORMATION

FOLFOX is a standard of care, FDA-approved regimen for the treatment of rectal cancer, and treatment will be provided and administered according to standard of care guidelines. More detailed information can be found in the products' package inserts.

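### Table 8.2's diarrhea hold, read literally, omits grade 2–4 diarrhea that persists despite antidiarrheals: a minor safety wording error in a guidance table

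*Combined protocol and SAP*

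**What the plan says.** Section 8.2 gives one table for both FOLFOX and CapeOx. It covers four toxicity categories: neutropenia, thrombocytopenia, diarrhea and other nonhematologic toxicities.

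The day-of-treatment entry for diarrhea has three sentences:

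1. The hold: "Hold chemotherapy if any grade of diarrhea above grade 1 is present with the patient not taking antidiarrheal agents within 24 hours of treatment".
2. The dose afterwards: "Reduce 5-FU and oxaliplatin 1 dose level upon resolution of diarrhea".
3. The limit: "If diarrhea has not resolved within 4 weeks of scheduled treatment day, discontinue therapy".

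The category for other nonhematologic toxicities says, for grades 3 and 4, "Hold until resolved to grade ≤1. Reduce 5-FU and oxaliplatin 1 dose level". Its heading exempts some toxicities, among them "nausea/vomiting if can be controlled by antiemetics".

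The introduction to section 8.2 sets the table's status. The modifications are strongly recommended, FOLFOX modifications are finally left to the treating provider, and readers are told: "Refer to table 8.2 and 8.3 for guidance regarding suggested dose reductions and treatment delays, consistent with best oncologic practices". Section 10 says of FOLFOX that "treatment will be provided and administered according to standard of care guidelines". Section 5.2 has patients examined "by a medical oncology physician or nurse with each cycle of chemotherapy".

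**The concern.** The first sentence joins a grade condition to a medication condition. If both must be true, taking an antidiarrheal removes the hold. Diarrhea above grade 1 in spite of medication is uncontrolled diarrhea, yet the sentence holds the unmedicated patient and is silent on the medicated one at the same grade.

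The clause was probably meant to say how the grade is to be judged: the patient should be at grade 1 or less without antidiarrheal help for 24 hours before being treated. The sentence does not say that.

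What is at stake is patient safety at the point of dosing. Chemotherapy begins 2 to 4 weeks after pelvic radiotherapy (section 7.1), and section 17 provides for participating sites that would work from the same table.

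**Working it through.** No figure in the plan depends on this sentence, so there is none to reproduce. The check is a reading of the text, followed by arithmetic on what a corrected rule would cost.

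**Step 1. The hold sentence by grade and medication use.**

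| Diarrhea on day of treatment | No antidiarrheal in prior 24 h | Antidiarrheal in prior 24 h |
|---|---|---|
| Grade 0–1 | no hold | no hold |
| Grade 2–4 | hold | no hold written |

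The lower right cell is the gap.

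**Step 2. The rest of the entry.** The reduction sentence sets the dose after resolution. The 4-week sentence counts from a scheduled treatment day and ends therapy if diarrhea persists. Both presuppose that treatment has been withheld. Neither orders it.

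**Step 3. The rest of the plan.** The next category is headed as covering other toxicities, so diarrhea, which has its own entry, falls outside it. Even if it were borrowed, it holds only grades 3 and 4, and grade 2 would still have no hold. Sections 7.1, 7.3, 8 and 10 contain no diarrhea hold.

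**Step 4. How the four categories treat the hold.**

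| Category | What triggers the hold | Does medication use alone lift it? |
|---|---|---|
| Neutropenia | ANC below 1000 | no |
| Thrombocytopenia | platelets below 75,000 | no |
| Other nonhematologic | grade 3–4, unless exempt; nausea/vomiting is exempt if controlled | no; for nausea/vomiting the test is control |
| Diarrhea | above grade 1 and no recent antidiarrheal | yes, read literally |

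One category of four lifts the hold on use of a medicine, whether or not it works.

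**Step 5. Dose cost of a corrected rule.** This is the price of the fix, not harm from the present text. Inputs are the schedules in sections 7.1 and 7.2, the dose levels in section 8.1, and the bar on re-escalation in section 8. Assume a single reduction to level −1 that takes effect at the earliest from cycle 2 and at the latest at the last cycle. Totals are in mg/m².

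| Agent | Planned total | Reduced from cycle 2 | Reduced at last cycle |
|---|---|---|---|
| FOLFOX oxaliplatin | 8×85 = 680 | 85 + 7×65 = 540 (−20.6%) | 7×85 + 65 = 660 (−2.9%) |
| FOLFOX infusional 5-FU | 8×2400 = 19,200 | 2400 + 7×1920 = 15,840 (−17.5%) | 7×2400 + 1920 = 18,720 (−2.5%) |
| FOLFOX bolus 5-FU, if used | 8×400 = 3200 | 400 + 7×300 = 2500 (−21.9%) | 7×400 + 300 = 3100 (−3.1%) |
| CapeOx oxaliplatin | 5×130 = 650 | 130 + 4×104 = 546 (−16.0%) | 4×130 + 104 = 624 (−4.0%) |
| Capecitabine (28 doses per cycle) | 5×28×1000 = 140,000 | 28,000 + 4×22,400 = 117,600 (−16.0%) | 4×28,000 + 22,400 = 134,400 (−4.0%) |

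**Step 6. Evaluability cost.** A patient who stops chemotherapy early is not evaluable under section 16.4 and is replaced. Section 16.6 plans 22 accrued and the target is 20, so the allowance is 22 − 20 = 2 patients.

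**The case against.** The strongest reply is that the sentence should be read with the two that follow it. Neither carries an antidiarrheal exception, and counting weeks from a scheduled treatment day makes sense only if treatment is being withheld until diarrhea resolves. On that view the drafting is loose but the intent is plain. This largely stands as an account of intent. It does not supply the missing instruction, because an implied hold is not a written one.

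The second reply is that the table is guidance. A provider may hold at any time, patients are seen each cycle, and FOLFOX follows standard of care. This also stands, and it is why the point is minor. Its reach is uneven: the discretion and standard-of-care sentences name FOLFOX only, although the guidance sentence covers the whole table. Freedom to depart from a recommended default does not make the default right.

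A third reply concerns the remedy. Simply deleting the antidiarrheal clause would let a patient be treated who is at grade 1 only because of medication, and that is less protective than the probable intent. This is correct, and the fix below keeps a 24-hour antidiarrheal-free condition for resuming.

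A reader might go further and infer that the protocol tells clinicians to treat through severe diarrhea. The documents do not support that. The text omits a hold for this case, and the neighbouring sentences point the other way. A reader might also count the ungraded word for resolution, or the absence of capecitabine from the reduction, as separate errors. The first is missing detail that the fix settles in passing. The second is editorial, since section 8.1 gives capecitabine dose levels and one dose level is therefore usable.

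**Conclusion.** The point holds as a minor patient-safety wording error. On a literal reading, grade 2–4 diarrhea that persists despite antidiarrheals has no written hold anywhere in the plan.

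Its size in patients cannot be stated, because the documents give no rate of such diarrhea and no measure of how often a clinician would treat through it. The dose percentages above describe the cost of correcting the rule and should not be read as harm. The endpoint definition, sample size and stopping rule are unaffected.

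The conclusion rests on two assumptions: that the hold sentence survived text extraction intact, as it appears to have done, and that its two conditions are read jointly. It makes no use of the blank entries beside the higher diarrhea grades in the worst-interval column, which may be merged cells lost in extraction. Many clinicians would hold anyway, so the practical effect is probably small.

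**What to change.** Replace the hold and reduction sentences in the diarrhea entry with:

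> Hold chemotherapy if diarrhea above grade 1 is present on the day of treatment, regardless of antidiarrheal use. Resume, reduced 1 dose level, when diarrhea is grade 1 or less without antidiarrheal agents for 24 hours.

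Keep the 4-week discontinuation sentence. If the sponsor meant complete resolution, it should state that stricter restart condition instead. Naming capecitabine beside 5-FU is an optional editorial addition.

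The change is one table entry in an amendment, with no added visits, tests or patients by design. It will cause some extra holds, and because re-escalation is barred, each resulting one-level reduction lasts. Occasionally a patient will reach the 4-week limit, stop therapy and use one of the two places allowed for inevaluable cases. That outcome is not automatic: the table is guidance, and section 7.1 sends cumulative delays beyond 4 weeks to the Principal Investigator for an individual decision. Where clinicians already hold in this situation, the hold itself adds no cost.
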